## 7.4 Dose Modifications

Modifying the dose of rtPA will not be permitted. However, should a patient's condition change such that their ventilation type is changed whilst receiving rtPA treatment (that is, from IMV to NIV, or vice versa) they will switch to the treatment schedule that is applicable to the new ventilation type.

If plasma fibrinogen levels fall to <1.0 g/L, the further dosing of rtPA in the patient will be stopped. Replacement therapy, either in the form of fibrinogen concentrate or cryoprecipitate will be administered to return fibrinogen to >1.0 g/L.

## 7.5 Visit schedule and assessments post initiation of treatment

### 7.5.1 Cohort 1 and 2

Any assessments that are done as per routine care do not need to be repeated.

- Documentation of respiratory status: Respiratory status of patients is monitored hourly and data points will be extracted for every four hours where available until 5 days after the last dose for cohort 1, but one data point per day is required as a minimum. For cohort 2 data will be extracted once a day coinciding with the worst PF ratio. As PF ratio is the primary endpoint, in addition to the worst PF ratio over the preceding 24 hrs up to a maximum of 6 data points spread across 24 hrs that represents patients clinical status will be extracted. Similar to cohort 1 respiratory data will be collected until 5 days after the last dose. After this period, respiratory status is to be documented weekly (+/- 1 day) until discharge, death, or 28 days whichever occurs first. The time of measurement should be documented.
- The variables include:
  - Details of oxygen and respiratory support including the type of device, FiO2 Respiratory rate
  - PaO2
  - For IMV patients, details of ventilation including but not exclusively the below
    - Tidal volume (in mL)
    - Full sedation or not – not for cohort 2
    - Paralysis or not – not for cohort 2.
    - Patient position – not for cohort 2
    - Peak inspiratory pressure (collected for computing compliance)
    - PEEP (collected for computing compliance)
  - For non-invasive oxygen support patients:
    - National Early Warning Score (NEWS 2) – not for cohort 2
    - Oxygen flow rate
    - SpO2
  - For CPAP patients
    - Positive end expiry pressure (PEEP)

The following tests are to be done at a minimum once a day until 5 days after the last dose (day 7 for SOC patients) in cohort 1, a minimum every other day in cohort 2, and then as required until day 28, discharge or death whichever occurs first.

- Local blood testing as per section 7.6.2

The following tests will be done once at 48 h (+/- 24 h) and 96 h (+/- 24h) after start of treatment and then twice weekly while on treatment until 5 days after stopping treatment. After this period, testing should be weekly (+/- 1 day) until day 28, discharge or death whichever occurs first. Twice weekly testing should be evenly spaced across weekdays if possible.

- Research blood sampling as per section 7.6.2

The following tests are to be done daily until 5 days after the last dose (day 7 for SOC patients), and then weekly (+/- 1 day) until day 28, discharge or death whichever occurs first:

- Directed physical examination at baseline, and thereafter weekly only in cohort 2
- vital signs (heart rate, temperature, blood pressure)
- Concomitant medications
- Review of Adverse events and Adverse drug reactions including bleeding episodes

The following assessments are to be done daily until 5 days after the last dose (day 7 for SOC patients) after the baseline assessments were done for these tests:

- Clinical status as assessed by a 7-point ordinal scale
- SOFA score
- Glasgow coma scale

The following end of study data will also be collected at day 28, discharge or death whichever occurs first:

- Documentation of any Oxygenation free days in the first 28 days
- Documentation of any Ventilator-free days in the first 28 days
- Incidence and duration of new oxygen use, non-invasive ventilation or high flow oxygen devices in the first 28 days.
- Documentation of incidence and duration of new mechanical ventilation use during the trial
  - Documentation of intensive care unit (ICU) free days in the first 28 days Death and cause of death (if applicable)
  - Documentation of any Oxygenation free days
  - Documentation of any Ventilator free days
- At 28 days on trial (or death or discharge, whichever comes first), a single measurement will be taken on the 7-point ordinal scale (see section 7.74)

### **7.5.2 Cohort 1 -Data collection for matched historical controls**

The following data will be collected for matched historical controls:

- Method of COVID-19 confirmation (PCR or radiological)
- Matching criteria (type of oxygen support, age, severity of disease according to  $\text{PaO}_2/\text{FiO}_2$  ratio, ethnicity, gender)
- COVID-19 admission history – to include PCR and CXR findings, date of admission to hospital, date of ICU admission, date of oxygen support and the progression of oxygen support to death or discharge from the study, presence or absence of pulmonary embolism and deep vein thrombosis. Presence of haemophagocytic syndrome will also be recorded, as this impacts on fibrinogen levels.
- Date of admission to hospital and duration of stay
- $\text{PaO}_2$

- $\text{FiO}_2$
- Patient position
- Ongoing 7-point ordinal scale
- Medical history – medical history to be reviewed and relevant history as assessed by the clinician to be recorded in the CRF, including an ISARIC style categorisation for all the major organ systems
- Concomitant medications
- SOFA score
- Glasgow coma scale
- Local blood results as per section 7.6.2
- Results from other standard of care assessments may also be collected if they explain the rate of change for the  $\text{PaO}_2/\text{FiO}_2$  ratio, such as secondary infections, medication changes.

This data will be collected where available for 28 days from the date of admission to hospital.

## 7.6 Laboratory Assessments and Procedures

### 7.6.1 Sample Collection

The Advisory Committee of Dangerous pathogens (ACDP) in conjunction with the Health and Safety Executive and Public Health England have classified COVID-19 as Hazard Group 3. Work with specimens that may contain the virus has been given dispensation to have diagnostic work carried out at less than full containment level 3 conditions subject to local risk assessment. The view of ACDP is that blood samples from confirmed COVID-19 patients can be handled in CL2 after local risk assessment of the possibility of aerosol generation for each kind of test/analyser.

### 7.6.2 Summary of laboratory tests

The following tests will be carried out at Local Laboratories as part of clinical care.

1. Confirmatory tests for coronavirus
2. Blood

Haematology	Full blood count including: haemoglobin, WBC, platelet count,
Serum chemistry	Routine clinical biochemistry including: renal, liver, bone, CRP, ferritin, LDH, BNP, troponin T (the last two baseline only)
Conventional coagulation tests	PT, APTT, Fibrinogen and D-dimers

3. Research blood tests

Procoagulants, anticoagulants, fibrinolytic proteins, fibrinolytic inhibitors, chemokines and cytokines

Research blood samples will be analysed in one of two laboratories:

1. Haemophilia research lab, Royal Free Hospital.
2. Department of Biochemical Sciences, University of Surrey, Guildford

Testing frequency will be presented in the schedule of assessments.

### 7.6.3 Storage of Sample Aliquots

Serum and plasma samples will be stored at in the Haemophilia and Thrombosis Laboratory Containment level 2 -80°C freezer prior to analysis and any additional analysis, the left-over aliquots will be stored in the Haemophilia and Thrombosis Centre Plasma Bank.

Samples for testing by University of Surrey will be shipped in batches. At the end of the trial, and on completion of all analyses, any remaining blood samples and the derivatives at University of Surrey thereof will be returned to CI for storage in Biobank/further analysis in ethics approved study.

Samples will be stored up to 5 years after the end of study for use in other ethically approved research projects.

## 7.7 Clinical Procedures and Data Collection

### 7.7.1 Directed physical examination:

A review of relevant body systems will be conducted by a study clinician. Vital signs will also be undertaken; these can be done by a clinician or study nurse. Vital signs include heart rate, temperature, blood pressure, and (at baseline only) body weight.

### 7.7.2 Review of medical history (including inpatient history and COVID-19 diagnosis) and document concomitant medications

A review of the patient's relevant medical history must be undertaken and documented in the medical notes and CRF. The patient's COVID-19 diagnosis (clinical or laboratory - confirmed by PCR or radiologically) must also be documented.

Inpatient history must include:

- Hospital admission time
- Hospital admission source (Community vs transfer from other institution)
- ICU admission time
- ICU admission source (ward/ED/OR/Transfer from other institution)
- Planned ICU admission (yes/No)

All over-the-counter or prescription medication, vitamins, and/or herbal supplements will be recorded.

### 7.7.3 Bleeding Episodes:

Bleeding episodes will be documented in the medical notes and CRF, and will include:

- Number
- Site, date and time of onset, Aetiology (spontaneous, traumatic, etc)
- Control of Anticoagulation Subcommittee of the International Society on Thrombosis and Haemostasis (Schulman and Kearon 2005) recommendation for major and minor bleeding will be implemented.
- Major bleeding in non-surgical patients is said to be present if the bleeding is
  - Fatal bleeding, and/or
  - Symptomatic bleeding in a critical area or organ, such as intracranial, intraspinal, intraocular, retroperitoneal, intra-articular or pericardial, pulmonary or intramuscular with compartment syndrome, and/or

- Minor bleed, if any sign or symptom of haemorrhage that does not fit ISTH definition of major bleed and one of (requiring medical intervention by a healthcare professional) leading to hospitalization or increased level of care prompting a face to face (i.e., not just a telephone or electronic communication) evaluation
- Any coagulation treatment required

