			
pulmonary or intramuscular with compartment syndrome.
 
therefore not including the following as a stopping criteria: 'Bleeding causing a fall in haemoglobin level of 20 g/L or more, or leading to transfusion of two or more units of whole blood or red cells.'
 
We have also added the caveat that the bleeding events specified in the stopping criteria should occur 'within start of treatment and 30 h after the last dose'.
 
Clinicaltrials.gov number added

5.0	20 May 2020		To update the rtPA dosing schedule and relevant endpoints
6.0	18 Sep 2020		
Use of historical matched controls instead of standard of care arm at a ratio of two controls to every one treatment arm.
 
Allowance for telephone consent for matched historical controls.
 
Use of deceased patients as historical controls with no consent sought.
 
Renaming of non-invasive ventilation group to non-invasive oxygen support arm (throughout protocol) and amended to include standard oxygen therapy.
 
Other small changes to the inclusion/exclusion criteria.
 
Extension of pre-treatment baseline period to 3 days.
 
Minor changes to primary and secondary (objectives and) endpoints.
 
Addition of University of Surrey laboratory for exploratory endpoint analyses.

7.0	11 Nov 2020		
To document that we will not be collecting consent for historical controls, following discussion with CAG.
 
Updates to data collected for historical control patients to allow for a more complete comparison between treatment patients and control patients (section 7.5.1). Also updates to the criteria to be used for matching of control patients to allow for better matching (section 10.4.2).
 
To make minor clarifications/corrections.

8.0	8 Jan 2021		To include an additional cohort of up to 30 patients to allow further accrual of safety and efficacy data.

9.0	14 Jan 2021	
To correct error in the wording in last row of dosing table for NIV patients (section 7.3.2) to clarify that dosing will continue every 12 h (+/- 2 h) on Days 6-14.
 
To make updates to schedule of assessments table in Appendix 1 (section 20) to further clarify assessments to be done in Cohort 2 (in line with updates made to section 7.5 in protocol version 8.0).

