Similarly in patients with acute myocardial infarction, the risk of intracranial haemorrhage is <1%, and in multivariable models the main risk factors were older age, female sex, black ethnicity, systolic blood pressure of 140 mm Hg or more, diastolic blood pressure of 100 mm Hg or more, history of stroke, tPA dose more than 1.5 mg/kg, and lower body weight (Gurwitz et al. 1998). In another study where the dose of r-tPA was investigated major or minor haemorrhagic events were associated with the extent of fibrinogen breakdown, peak rtPA levels, thrombocytopenia, prolongation of the activated partial thromboplastin time (APTT) to more than 90 seconds, weight of 70 kg or less, female gender, and physical signs of cardiac decompensation (Bovill et al. 1991). The outcomes in patients with stroke and acute myocardial infarction, is related to both the indication for thrombolysis and potentially fatal brain haemorrhages.

The other common site of bleeding is gastrointestinal bleeding, which is often not fatal and can be managed as per standard protocols. There has been an increasing interest in catheter directed thrombolysis over extended duration in venous thrombosis to decrease the risk of bleeding with

potential similar efficacy. In a randomised trial of pharmacomechanical-thrombolysis, in the treatment group major bleeding was seen in 1.7% of patients (6 of 336 treated patients) which consisted of two patients with gastrointestinal bleeding, two patients with retroperitoneal bleeding and two patients with bleeding at the site of the procedure. All patients were receiving concomitant anticoagulation (Vedantham et al. 2017). In another retrospective registry of around 500 patients, one intracranial haemorrhage was seen with the majority of major bleeding limited to the site of procedure.

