In total, 7 bleeding events were identified. A bleed was considered not related to alteplase if the event happened 30 hrs after the last dose of treatment, alteplase exposure time period. Six of the seven bleeds were beyond alteplase exposure time period, and one was within the time period.

One bleed each met the criteria for ISTH major and minor bleed. Five bleeds did not meet the ISTH criteria for minor or major bleeds. The severity of bleeds as assessed for adverse event reporting resulted in five bleeds being categorised as mild and two events as moderate.

The severity assessment as used for AE reporting was used to further describe the bleeds.

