6.3 Analysis of primary outcome

The primary outcome for efficacy is oxygenation, measured using the PaO₂/FiO₂ ratio over time. The distributions of the primary outcomes will be summarised, by group, over time. Change in PaO₂/FiO₂ ratio from baseline will be checked visually using means & SE plots. If necessary, appropriate transformations of the data will be performed (e.g., using the natural logarithm).

Subject to the final sample size and data quality, PaO₂/FiO₂ ratio will also be compared between the SOC group (historical controls) and rtPA group using appropriate regression modelling, controlling for baseline oxygenation ratio:

$$OXY_i = \beta_0 + \beta_1 \cdot T_i + \beta_2 \cdot OXY0_i + \varepsilon_i,$$

where the i subscript denotes the i^{th} patient and

- OXY_i = PaO₂/FiO₂ ratio (oxygenation) at the end of treatment;
- T_i = group indicator (= 1 if patient is in the rtPA group, = 0 otherwise);
- $OXY0_i$ = PaO₂/FiO₂ ratio (oxygenation) at baseline;
- $\varepsilon_i \sim N(0, \sigma^2)$ = Normally distributed error term.

The estimate of the parameter β_1 and associated 95% confidence interval shall be reported, as well as a p-value pertaining to the hypothesis test of

$$H_0: \beta_1 = 0 \text{ versus } H_1: \beta_1 \neq 0.$$

Similarly, the use of models using oxygenation at other meaningful timepoints as outcome measure will be evaluated. Owing to a limited sample size, models shall not adjust for other baseline characteristics. Fitted models shall be checked, where appropriate, to ensure that modelling assumptions have been satisfied. Appropriate transformations of outcomes or other suitable approaches (e.g., robust or non-parametric methods) shall be explored if model assumptions are not satisfied.

For treatment safety, the incidence and severity (either major or minor) of bleeding events will be summarised with frequencies and percentages in each group. Fibrinogen levels will also be summarised graphically using plots of the mean, by group, over time. Finally, the number and nature of serious adverse events (SAEs) will be summarised. These events are defined in section 8 of the protocol.

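### SAP 6.3 has no category for 5 of the 7 bleeds reported in cohort 1, and the major-bleed list in protocol 7.7.3 is incomplete as printed

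*Protocol*

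**What the plan says.** - **Endpoint.** Protocol 10.1.2 makes major bleeding attributable to the drug a primary safety endpoint. The SAP's summary table says the same; SAP 5.1 lists major bleeding without the attribution condition.
- **Analysis.** SAP 6.3, on the primary outcome, states that "the incidence and severity (either major or minor) of bleeding events will be summarised with frequencies and percentages in each group". It gives no third grade.
- **Major bleeding.** Protocol 7.7.3 adopts the ISTH recommendation. It then prints two limbs, fatal bleeding and symptomatic bleeding at a critical site. The second ends "pulmonary or intramuscular with compartment syndrome, and/or" and the next bullet is about minor bleeding.
- **Minor bleeding.** In the same section, a bleed is minor if it is not ISTH major and also meets one of some further conditions. These are run together: medical intervention, hospitalisation, and "increased level of care prompting a face to face (i.e., not just a telephone or electronic communication) evaluation".
- **Data so far.** Protocol 2.7 reports on the 9 treated cohort 1 patients: "In total, 7 bleeding events were identified". "One bleed each met the criteria for ISTH major and minor bleed". "Five bleeds did not meet the ISTH criteria for minor or major bleeds".
- **Version log, v4.0.** The log records a limb taken out of the trial stopping criteria, where it had stood under ISTH major bleeding: "Bleeding causing a fall in haemoglobin level of 20 g/L or more, or leading to transfusion of two or more units". It does not mention the endpoint.

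**The concern.** There are two separate problems.

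The first is the table. A two-grade scale works only if every bleed that is not major is minor. The protocol's minor grade is not a remainder category, because it has conditions of its own. A bleed can therefore be neither, and most cohort 1 bleeds were. A statistician following SAP 6.3 must leave those bleeds out or call them minor, and the SAP does not say which.

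The second is the grading text. The printed major-bleed list does not contain the haemoglobin and transfusion limb that the sponsor's own log attributes to ISTH. Nor do the items that 7.7.3 asks to be recorded for a bleed mention haemoglobin fall or units transfused, so nothing there prompts a grader to apply it. Protocol 2.6 says of the thrombolysis literature: "The other common site of bleeding is gastrointestinal bleeding, which is often not fatal". A bleed of that kind could be major through haemoglobin or transfusion alone.

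The minor criteria are also hard to apply here. All participants are inpatients on oxygen or ventilation, so hospitalisation and bedside review do little to separate one bleed from another.

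The stakes are practical. Bleeding is the only non-serious adverse event collected in the case report form (8.2), and the DMC advises on progression to a randomised trial from these data (12.2). Cohort 2 also drops the cohort 1 exclusions for bleeding disorders and recent active bleeding (6.1.2 against 6.1.4).

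**Working it through.** **Inputs** (protocol 2.7, preliminary, 9 treated patients): 7 bleeds; 1 ISTH major, 1 ISTH minor, 5 neither; 5 mild and 2 moderate on the adverse-event scale; 6 outside the exposure window and 1 inside. Section 2.5 adds that none was considered related to the drug.

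**Reproducing the plan's total.**
- ISTH class: 1 + 1 + 5 = 7
- Adverse-event severity: 5 + 2 = 7
- Exposure window: 6 + 1 = 7

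All three splits agree with the stated 7.

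**Fitting these bleeds to the SAP 6.3 scale.** Percentages are of bleeds, not of patients.
- Bleeds without a category: 5/7 = 71.4%

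| Rule | Major | Minor | Neither | Bleeds shown |
|---|---|---|---|---|
| Two grades, unclassified bleeds omitted | 1 | 1 | no row | 2 of 7 |
| Two grades, every non-major bleed called minor | 1 | 1 + 5 = 6 | no row | 7 of 7 |
| Three levels | 1 | 1 | 5 | 7 of 7 |

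As a share of all 7 bleeds, minor is 1/7 = 14.3% under the protocol's own grading and 6/7 = 85.7% if non-major is taken to mean minor. Only the three-level row reproduces section 2.7.

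**Effect of the missing limb.** This cannot be computed, because haemoglobin and transfusion data for each bleed are not in the text available. If the limb was not applied in cohort 1, restoring it could add between 0 and 6 majors to the 1 reported. The bounds are therefore 1 to 7, and they are logical limits, not estimates. If the limb was applied, nothing changes.

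**Effect on the protocol's endpoint.** Attributable majors are bleeds that are both major and related. None of the 7 was considered related, so the count is 0 whatever the grading. SAP 5.1 omits attribution, so a count made on that wording would depend on the grading alone.

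**The case against.** The strongest reply is that the definition has not changed. Section 7.7.3 adopts ISTH by reference, and its minor criterion defers to the ISTH definition of major bleeding. Section 2.7 says the ISTH classification was used for cohort 1. A list that stops at a conjunction looks like an omission, or text lost when the PDF was read, and not like a decision. The v4.0 log concerns stopping criteria only and cannot show that the endpoint was narrowed.

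A reader might still infer that the limb was deliberately dropped and that major bleeding has been under-counted. The documents support neither. What evidence there is may even point the other way: one bleed was ISTH major, yet all seven were graded mild or moderate, and 8.3.1 describes moderate as not damaging to health. That sits awkwardly with a fatal or symptomatic critical-site bleed, and more easily with the haemoglobin or transfusion limb having been applied. This too is inference and settles nothing.

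Other points also stand. The minor count is not part of the protocol's primary safety endpoint. Bleeds are collected as events of special interest (8.2) and all study data are to be listed (10.6), so no event need disappear from the record. All analyses are descriptive. SAP 1.0 was written for protocol 7.0, and a separate SAP is planned for cohort 2. Investigators did separate minor from neither in practice, so the minor grade is not unworkable.

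None of this repairs the SAP table, which still has two grades for data that fall into three. Nor does it show a later grader what to do with a list that breaks off, or which reading of the run-together minor criteria produced five bleeds that were neither.

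**Conclusion.** The point holds in two parts.

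**SAP 6.3 is wrong as written.** Its scale cannot hold 5 of the 7 reported bleeds (71%), and the minor count is 1 or 6 depending on a rule it does not give. This rests only on the counts in section 2.7, which are labelled preliminary. It affects the safety table in the SAP's primary-outcome section, not the protocol's attributable-major endpoint.

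**Protocol 7.7.3 is incomplete as printed.** The consequence is conditional: if graders use the two printed limbs literally, a non-fatal bleed outside a critical site that is major only by haemoglobin fall or transfusion would not be counted as major. Whether this has happened cannot be told from the documents. The preliminary attributable-major count for cohort 1 is 0 either way, so a claim that the trial's major-bleeding result is already too low is not supported.

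The matter is more than a missing detail, because correcting it changes the counts shown in the SAP table and removes a possible misgrading in cohort 2.

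**What to change.** 1. **SAP 6.3 and the cohort 2 SAP.** Replace the two grades with three levels: ISTH major, ISTH minor, and neither. Count all bleeds, and cross-tabulate the levels with the mild, moderate and severe grade of protocol 8.3.1, which already classified all seven.
2. **Protocol 7.7.3, major bleeding.** Reconcile the printed endpoint definition with the ISTH recommendation it cites, including the haemoglobin and transfusion limb that the v4.0 log attributes to ISTH. Otherwise, state explicitly that the limb is excluded from the endpoint. Keep this separate from the stopping list in 7.10, which this point does not ask to change.
3. **Protocol 7.7.3, minor bleeding.** Repunctuate the criteria so that each condition stands alone, and say how each applies to someone already in hospital.
4. **Cohort 1.** Confirm that the seven bleeds were graded on one and the same definition, and say which.

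The cost is wording in two documents and a check of seven records. Haemoglobin is already among the local blood tests (7.6.2); units transfused would come from the medical records. The one downside is that the reported major-bleed rate may turn out slightly less favourable.
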